## Research Objectives:

- 1) To determine the effectiveness of a PT-led primary care model for people with hip and knee pain at

improving function (primary outcome), pain intensity, quality of life, global rating of change, patient satisfaction, and adverse events compared to usual physician-led primary care, when evaluated over a one-year period from the initial consultation.

2) To assess the impact of a PT-led primary care model for patients with hip and knee pain on the health system and society (healthcare access, primary care physician workload, healthcare utilization, missed work, cost-effectiveness), evaluated over a one-year period from initial consultation.

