## Methods

**Design:** The trial is a parallel arm cluster randomized controlled trial (RCT) conducted across 14 primary care sites in Ontario, Canada. Participating sites were randomized 1:1 to either a PT-led primary care model or the usual physician-led primary care model for hip and knee pain. Randomizing at the practice level, rather than the patient level, enabled full integration of PTs within the primary care team and minimized the risk of contamination between providers. This protocol and analysis plan is according to the Standard Protocol Items: Recommendations for Interventional Trial (SPIRIT) reporting guidelines. See Table 1 for an overview of the schedule of enrolment, interventions and assessments as recommended in the SPIRIT guidelines.

Table 1. Schedule of enrolment, interventions, and assessments.

	STUDY PERIOD						
	Enrolment or clusters	Allocation of clusters	Enrolment of patient participants	Post-allocation			Close-out
TIMEPOINT	Pre-intervention	Pre-intervention	0 (baseline)	3 mo.	6 mo.	9 mo.	12 mo.
ENROLMENT OF PRIMARY CARE SITES:							
Eligibility screen	X						
Informed consent	X						
Allocation to study group		X					
ENROLMENT OF PATIENT PARTICIPANTS:							
Eligibility screen			X				
Informed consent			X				
INTERVENTIONS:							
PT-led primary care				◆	—————→		
Usual care				◆	—————→		
ASSESSMENTS:							

Participant characteristics and demographic information			X				
Participant health and experiences outcomes (LEFS, pain intensity, EQ-5D-5L, PSEQ, PCS, TSK-11, PHQ-2)			X	X	X	X	X
Participant health and experiences outcomes (GROC, satisfaction, adverse events)				X	X	X	X
Health system and societal outcomes (provider encounters, EHR utilization, healthcare utilization, missed occupational activities, assistance required)				X	X	X	X
Implementation measures (timely access, PT as first point of contact, access to PT, hip/knee management)			X	X	X	X	X
Implementation measures (patient adherence)				X			
QUALITATIVE INVERVIEWS:							
Patient participants				X			

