## **1. Baseline Characteristics Used to Describe the Population**

We collected the following baseline information from participants through REDCap: age, sex, gender, education, duration of hip/knee pain, locations of pain, medications, comorbidities, employment status, income, rurality, and ethnicity. Comorbidities are assessed using the Functional Comorbidity Index (a list of comorbidities that are associated with physical functioning. The presence of a comorbidity is assigned a score of 1 and the total score is the sum of the comorbidity element with a maximum score of 18).

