### 3. Health System Outcomes

Primary care physician or nurse practitioner visits: the total number of patient visits, both initial and follow-up, related to hip or knee pain. This metric is being used to explore whether involving PTs in care delivery helps alleviate demand on primary care providers, potentially allowing them to allocate more time to patients with other health concerns.

Healthcare utilization within the primary care team: consultations with all primary care team members (e.g., physicians, nurse practitioners, nurses, social workers, and occupational therapists), including the PT in the intervention sites, and group programming accessed within the organization. This data is being collected from the EHR abstraction process.

Healthcare utilization outside of the primary care team: medications used; walk-in clinic visits; ED visits; inpatient hospital stays; diagnostic imaging; surgeries, injections, and other interventional procedures; visits to specialist physicians; and visits to other health professionals outside the primary care team (e.g., chiropractors, massage therapists, occupational therapists, physiotherapists, chronic pain clinics). These outcomes are being collected from the self-report surveys at each follow-up assessment and verified, whenever possible, in the EHR.

Missed Occupational Activities: self-reported time lost from paid employment, volunteer, homemaking, or educational activities.

Assistance required: self-reported paid and unpaid assistance required. For example, self-care (e.g., taking medications, dressing/undressing, going to the bathroom, bathing/showering, grooming), shopping/groceries, meal preparation, housework, managing finances, or transportation (e.g., to a medical appointment).

**Costs:** Total per-person costs include both direct and indirect healthcare costs, with indirect costs estimated using a human capital approach based on time missed from work or other daily activities.

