**Data Analysis Plan**

All analyses will be by intention to treat principle. Descriptive statistics will be provided for baseline characteristics and outcomes using means (standard deviation) or medians (interquartile range) for continuous variables and frequencies (percent) for categorical variables. We will compare arms using linear mixed models and generalized estimating equations (GEE) to account for clustering and present the corresponding p-values. Analyses will be performed using SAS, version 9.4 (SAS Institute Inc; Cary, NC).

The estimand for patient health outcomes will be the time-specific patient participant treatment effect, adjusting for clustering by primary care site. The primary outcome (LEFS) will be analyzed using linear mixed regression with restricted maximum likelihood (REML) estimates under the assumption of Missing at Random (MAR), which will allow the use of all available data without the need for multiple imputation. The Kenward-Rogers degrees of freedom correction will be used to account for a small number of clusters. The 12-month timepoint will provide the intervention effect as the adjusted least square mean difference between arms with 95% confidence intervals. Secondary comparisons will be made using adjusted least square mean differences between arms at all intermediate time-points. Fixed effects in the mixed model will include time, intervention group by time interaction (omitting the group main effect), pre-specified covariates associated with hip and knee function (patient participant age, sex, duration of current episode of hip or knee pain, income, highest level of education, and comorbidity score), and primary care site rurality and number of active patients (the covariates from the covariate-constrained allocation procedure). Repeated measures will be modeled using a covariance structure determined by information criteria (AIC/BIC). Clinic site will be included as a random effect to account for site clustering. We will assess for potential risk of bias associated with missing data by comparing the characteristics of those who participated. We plan to carry out a sensitivity analysis for a potential departure of our MAR assumption using a delta-adjusted imputation pattern mixture model approach. This approach will allow us to investigate the robustness of our trial outcomes with regard to the missing values of the LEFS.

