to account for small number of clusters. Given that we have only included 14 clusters and adverse events are expected to be rare, we anticipate there may be issues of non-convergence or instability in our models. Should the model for adverse events not converge or demonstrate instability, we would attempt to fit the model using an independent working correlation matrix. If there are still issues of non-convergence or instability, we will reduce the model by removing covariates, beginning with duration of pain and income. Severity and duration of minor adverse events will be presented descriptively. We do not anticipate many, if any, serious adverse events; as such, we plan to present these data descriptively.

Visits with primary care physicians or nurse practitioners, time (days) lost from occupational activities, and assistance required (hours) will be presented as rates and compared by calculating rate ratios using GEE-type covariance estimators with an adjusted Poisson or negative binomial model, accounting for clustering, and assuming an exchangeable working correlation matrix. Incidence rates will be used to present visits to other health professionals within the primary care team, participation in group programs offered by the primary care team, and health care services received outside of the primary care team (medications, diagnostic imaging, walk-in clinic visits, ED visits, specialist physician visits, , hospital admissions, interventional procedures, surgeries, other health provider visits). Comparisons between groups for each of these variables will be made by calculating relative risk using robust Poisson regression. These models will incorporate empirical covariance (“sandwich”) bias-adjusted (residual-based) estimators, and the Fay and Graubard correction due to the small number of clusters. These models will use time as an offset to account for variable follow-up times. All of the healthcare utilization and lost time from occupational activity models will control for the same covariates as the patient health outcomes analyses. Similar to our analyses for adverse events, in the case of model non-convergence or instability, we will attempt to fit the model using an independent working correlation matrix and if the model still does not converge and demonstrate stability, we will reduce the model by removing covariates.

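### The lost-time model omits baseline employment status, and its only between-arm rate comparison pools paid with unpaid time although missed work is a stated objective

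*Combined protocol and SAP*

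**What the plan says.** Under Research Objectives, the second objective covers effects on the health system and society, listed as "healthcare access, primary care physician workload, healthcare utilization, missed work, cost-effectiveness". Section 3, Health System Outcomes, defines the corresponding measure as "self-reported time lost from paid employment, volunteer, homemaking, or educational activities". The Data Analysis Plan expresses days lost from occupational activities as one rate and compares arms by a rate ratio from an adjusted Poisson or negative binomial model that allows for clustering.

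On adjustment, the same section says: "All of the healthcare utilization and lost time from occupational activity models will control for the same covariates as the patient health outcomes analyses". The list referred to is the one for the LEFS model. At patient level it is introduced as "pre-specified covariates associated with hip and knee function (patient participant age, sex, duration of current episode of hip or knee pain, income" and goes on to education and comorbidity score. At site level it adds "primary care site rurality and number of active patients". That makes eight covariates.

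Section 1, Baseline Characteristics, shows that more was collected, including "locations of pain, medications, comorbidities, employment status, income, rurality, and ethnicity". Employment status and medications appear in no planned model.

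**The concern.** A list chosen to predict function need not suit days lost from work. Paid days can be lost only by people in paid work. That follows from the definition of the outcome and needs no outside prognostic data.

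Carrying the list over also does not carry over the baseline adjustment that LEFS enjoys. LEFS is measured at baseline and enters its model as a repeated measure with no group main effect. The schedule in Table 1 marks the health system and societal outcomes ("provider encounters, EHR utilization, healthcare utilization, missed occupational activities, assistance required") only at 3, 6, 9 and 12 months, so lost time has no baseline value. Employment status is the nearest substitute available.

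Two things are at stake. With 14 sites, allocation constrained only on rurality and number of active patients, and patients enrolled after allocation, the arms may differ in the share employed, and part of that difference would pass into the rate ratio. Separately, a pooled rate can hide or dilute an effect on paid work, which is what a reader of Objective 2 would expect to see reported.

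**Working it through.** The plan gives no figure for lost time. Its only power calculation is for LEFS and does not bear on this point, so there is nothing to reproduce. The figures below are illustrations on assumed values, and none includes covariates.

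**1. Covariates against data collected.** In the model: age, sex, duration of current episode, income, education, comorbidity score, site rurality, number of active patients. Collected at baseline but not in the model: employment status. Age and income are partial proxies. If a model fails to converge, covariates are removed. For adverse events, duration of pain and income go first; the utilisation and lost-time rule is described as similar but names no order.

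**2. Effect of an employment gap when there is no treatment effect.** Let e1 and e0 be the shares employed in the two arms, and let employed participants lose k times as many days as others. The unadjusted null rate ratio is

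RR = (e1·k + 1 − e1) / (e0·k + 1 − e0).

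Ten-point gap, 50% against 40%:
- k = 2: 1.5/1.4 = 1.07
- k = 3 (for example 6 against 2 days a year): 2.0/1.8 = 1.11
- k = 4: 2.5/2.2 = 1.14
- k = 8 (for example 8 against 1 day): 4.5/3.8 = 1.18

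Ten-point gap, 45% against 35%, k = 8: 4.15/3.45 = 1.20.

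Five-point gap, 45% against 40%, k = 2, 4, 8: 1.45/1.4 = 1.04, 2.35/2.2 = 1.07, 4.15/3.8 = 1.09.

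With the arms reversed, the ten-point range becomes 1/1.20 = 0.83 to 1/1.07 = 0.93.

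**3. How unusual a ten-point gap is by chance.** Inputs: 7 sites per arm and 560/14 = 40 participants per site (Study Power); an assumed overall share employed p = 0.42; an assumed ICC for employment of 0.02 to 0.10. With equal site sizes,

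SD = √{2·p(1 − p)·[1 + (m − 1)·ICC]/(7m)}, with p(1 − p) = 0.2436 and m = 40.

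- ICC 0.02: design effect 1.78, SD 5.6 points
- ICC 0.05: design effect 2.95, SD 7.2 points
- ICC 0.10: design effect 4.90, SD 9.2 points

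Taking the plan's coefficient of variation of 0.7 as that of site size, the design effect is 1 + (1.49 × 40 − 1)·ICC = 2.17, 3.93 and 6.86, and the SD is about 6.1, 8.3 and 10.9 points. Ten points is therefore about 1.1 to 1.8 SD with equal sites and about 0.9 to 1.6 SD with unequal sites: plausible by chance, but not expected.

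**4. Dilution by pooling.** Suppose the rate ratio is 0.70 for paid days and 1.00 for unpaid days, and paid days make up a share s of days lost in the usual care arm. The pooled ratio is 0.70·s + (1 − s): 0.94, 0.88, 0.82 and 0.76 for s = 0.2, 0.4, 0.6 and 0.8.

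**The case against.** The best defence is that this is a choice, not an error. The covariates are pre-specified and openly stated. Under randomisation, leaving out a prognostic variable costs mainly precision, and chance differences between sites are part of the variation that the clustered variance is meant to reflect. Recruitment after allocation could add bias, but the plan describes consecutive invitation, identical information and disclosure of arm only after consent, and nothing suggests selection on employment. All of this stands. A reader might infer that the lost-time comparison is biased as planned, or that 1.07 to 1.20 is the error to expect from it. The documents support neither: those ratios come from a formula with no covariates, and the planned model adjusts for eight.

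A reader might also infer that paid work is never separated from unpaid activity. That is wrong for the plan as a whole. The costing text values the two separately, and costs are to be reported in disaggregated form. Nor is counting unpaid roles a fault, since it includes participants without paid jobs. What remains is that neither costing step compares paid days between arms.

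A third tempting extension is that every utilisation model is deficient for want of baseline medication. That reaches too far. Baseline medication bears mainly on the medication outcome, one of many. Some patients were identified during a clinical visit, with consent and the baseline survey afterwards, so a drug started at that visit could be recorded as baseline and adjusting for it could remove part of the effect.

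Finally, the plan anticipates unstable models with 14 clusters and would drop covariates in response. This does not defeat the employment change. The stated worry concerns rare adverse events, lost time is not expected to be rare in that sense, and one covariate is being added to eight under a fallback rule that already exists.

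**Conclusion.** The point holds for the lost-time outcome. The model reuses a function-based covariate list, omits a collected variable that determines who can lose paid days, and offers no between-arm rate comparison of paid work although missed work is a named objective. The consequence is mainly lost precision and exposure to chance or recruitment imbalance.

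The size is a null rate ratio of about 1.07 to 1.20 for a ten-point gap in employment, and 1.04 to 1.09 for a five-point gap. This rests on assumed employment shares, on employed participants losing two to eight times as many days as others, and on no adjustment. Age, income and comorbidity would reduce it by an amount the documents do not allow one to calculate. The dilution figures also rest on assumed effects. This is a cheap improvement on a secondary outcome, not a defect in the main result.

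**What to change.** Make these changes in the Data Analysis Plan before analysis starts. The plan is dated November 20, 2025, and analysis is to begin only after data collection, expected to end by December 19, 2025.

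1. Add baseline employment status to the covariates of the lost-time model.
2. Add a secondary model of paid-work days lost among participants employed at baseline, and report it next to the composite.
3. If baseline medication is used at all, confine it to a sensitivity analysis of the medication outcome, and note that the baseline survey may follow the index visit.

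The cost is one more covariate and one model on a smaller sample, both subject to the existing rule for non-convergence. Employment status is already collected. The paid-days model requires that the follow-up surveys record paid time separately, which the separate costing of paid and unpaid time presupposes. Introduced after results are known, the same analyses would be post hoc.

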A common concern in cluster RCTs is the risk of selection and recruitment bias, particularly when patient enrollment occurs after cluster assignment. To address this, we took efforts to invite consecutive patients with hip or knee pain to participate in the study, to ensure RAs who handled recruitment and consent were not familiar with the patients, and to apply inclusion and exclusion criteria consistently across all sites. We also provided identical trial information to all potential participants before obtaining consent, regardless of cluster. This meant that we did not reveal which study arm participants were in until after obtaining their consent.

**Patient Participant Recruitment:** During patient participant recruitment, medical secretaries screened patients to be invited to participate when they booked an appointment for hip or knee pain. As an additional strategy, potential participants were also identified any healthcare provider (HCP) when they sought care for their hip or knee pain during a clinical visit. Potential participants who were agreeable to being invited to participate were contacted by a study research assistant (RA) to explain the details of the study. Those who were interested in participating were asked to complete a consent form that was built into the baseline surveys in a secure data collection platform (REDCap, Research Electronic Data

Capture). If a potential participant requested to do this in-person, arrangements were made to meet with the RA who provided detailed written and verbal information about the study and obtained consent for participation from those patients who were interested. A verbal consent process was in place for those who preferred to do this over the phone or in a virtual meeting.

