**Inclusion/Exclusion:** All adult ( $\geq 19$  years) patients who sought primary care for their hip or knee pain of any duration at participating sites were invited to meet with the RA to discuss participating in the study. Potential participants were excluded if: they reported not being able to understand, read, and write English; they had known cancer causing their hip or knee pain; or they reported being unable to complete the scheduled follow-up surveys over the one-year study period. The inclusion criteria for primary care sites were to have at least 1,500 rostered patients and two or more family physicians. Those sites that already had physiotherapy services or not enough space to include the physiotherapist were excluded.

**Study Power:** Participants were recruited over a 13-month period at all 14 primary care sites (7 PT-led arm, 7 usual care arm). Our power calculation is based on methods described by Hemming et al. Our sample size calculation is targeted to detect a clinically meaningful mean difference of 9 points on the Lower Extremity Functional Scale (LEFS) using a two-sided alpha of 0.05, assuming a conservative standard deviation of 16, a conservative intracluster correlation coefficient of 0.1, a cluster autocorrelation coefficient of 0.5, an individual autocorrelation coefficient of 0.6, and a coefficient of variation of 0.7. Allowing for an attrition of 20% of patient participants at the 12-month follow-up, we require a sample size of 560 participants to achieve  $>80\%$  power. Pilot work for this study suggested we would recruit 1 patient per week per site; as such, we planned and prepared resources to recruit approximately 728 participants.

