## **2. Individual Health and Experience Outcomes**

The following individual health and experience measures are being collected through REDCap with repeat surveys at baseline, 3-, 6-, 9-, and 12-months post enrollment. Patient satisfaction, global rating of change, and adverse events are being collected at all follow-up time points only.

- Self-reported functioning: using the LEFS – a validated 20-item patient-reported outcome measure used to assess functional status related to lower extremity conditions. Each item is scored on a 5-point scale, with higher scores indicating better function.
- Pain intensity: measured using a Numeric Pain Rating Scale (NPRS) where 0 is no pain and 10 is the worst possible pain.
- Health-related quality of life: using the EuroQOL-5D (EQ-5D-5L), which is suitable for economic evaluations. The EQ-5D-5L score will also be converted to quality-adjusted life years (QALY).
- Global rating of change: using an 11-point global rating of change (GROC) scale to assess perceived overall change in health status, symptoms, or function over time, with anchors of a great deal better (+5) to a great deal worse (-5).
- Patient satisfaction: using an 11-point scale with anchors of very dissatisfied (-5) and very satisfied (+5).
- Adverse events: using an adverse events questionnaire aligned with reporting guidelines. The questionnaire determines: 1) adverse events experienced as a result of any of the interventions received; 2) a description of the adverse event; 3) duration of the adverse event; and 4) severity of the adverse event. Serious adverse events are identified if the participant requires hospitalization or an emergency department as a result of the adverse event, the adverse event leads to significant and persistent disability beyond 72 hours, or the adverse event is life-threatening. The study team monitored these responses to ensure ongoing patient participant safety.
- Potential mechanisms of the intervention:

- Self-efficacy: confidence in abilities to participate in usual activities using the Pain Self-Efficacy Questionnaire (PSEQ).

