Our cost utility analysis will be carried out from societal (primary) and health payer (secondary) perspectives. We will calculate total costs by multiplying the quantity of resource use by the corresponding unit cost, summing the total cost over each follow-up interval to determine total costs at each follow-up time point as well as across the entire study period. Total and mean costs (overall and at each time point) will be presented by aggregated and disaggregated costs. We will estimate quality adjusted life year (QALYs) for every participant using area under the curve and assuming linear interpolation between assessment time points. Bivariate multilevel modelling, accounting for clustering, will be used to analyze the incremental cost per Quality-Adjusted Life Year (QALY) gained and describe the incremental net benefit at various values of willingness-to-pay. We will model treatment group as a fixed effect and account for site clustering. We will adjust for the same covariates as the primary analyses. We will use a probabilistic sensitivity analysis with Monte Carlo simulations to explore the uncertainty in our cost-effectiveness estimates. The results will be illustrated on cost-effectiveness planes, and cost-effectiveness acceptability curves will be presented to demonstrate the likelihood that the PT-led care model is cost-effective across various willingness-to-pay thresholds.

We also plan a subgroup analysis based on sex for each of our effectiveness outcomes, as recommended in the sex and gender equity in research (SAGER) guidelines. We will include an interaction term with sex and group, and group by time in order to assess this. We will present the data using forest plots and 95% confidence intervals.

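### The cost-utility model does not adjust for baseline EQ-5D-5L utility, so part of any baseline imbalance passes into the QALY difference and precision is lost

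*Combined protocol and SAP*

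**What the plan says.** The cost-utility paragraph of the Data Analysis Plan estimates QALYs "for every participant using area under the curve and assuming linear interpolation between assessment time points". Costs and QALYs then go into a bivariate multilevel model, of which it says "We will model treatment group as a fixed effect and account for site clustering" and "We will adjust for the same covariates as the primary analyses".

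The primary-analysis covariates are given earlier in the same section: "patient participant age, sex, duration of current episode of hip or knee pain, income, highest level of education, and comorbidity score", together with site rurality and number of active patients. Neither baseline LEFS nor baseline EQ-5D-5L is on the list.

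The primary model deals with baseline in another way. Its fixed effects contain time and the "intervention group by time interaction (omitting the group main effect", so the baseline score is one of the repeated outcomes and both arms share a common baseline mean. The EQ-5D-5L effectiveness analysis takes over that whole approach.

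EQ-5D-5L is collected in "repeat surveys at baseline, 3-, 6-, 9-, and 12-months post enrollment", so baseline utility will be available. Nothing in the document adds it to the economic model.

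**The concern.** The cost-utility paragraph imports the covariates of the primary model but not its structure. A model for one QALY total per person, with a main effect of group, has no baseline row to constrain. The plan therefore protects EQ-5D-5L against baseline imbalance as an effectiveness outcome, but not the QALY built from the same scores.

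Baseline utility enters the QALY twice: as the first point of the curve, and through its correlation with every later point. An arm that starts with higher utility will show more QALYs even if the intervention does nothing.

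This trial is exposed to such imbalance. It has seven sites per arm, the constrained allocation balanced only number of active patients and rurality, and patients enrolled after allocation. Cost-effectiveness is part of the second research objective. At stake are the incremental net benefit, the cost-effectiveness plane and the acceptability curves.

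**Working it through.** **The plan's own figure.** The plan gives no figure for the cost-utility analysis. Its only calculation is 560 participants for more than 80% power on the LEFS. That is 560/14 = 40 per site, or 32 after 20% attrition. With ICC 0.1, CV 0.7 and m = 32:
- design effect = 1 + (1.49 × 32 − 1) × 0.1 = 5.668
- r = (32 × 0.1 × 0.5 + 0.9 × 0.6)/(1 + 31 × 0.1) = 0.522
- variance of the difference = 2 × 16² × 5.668 × (1 − 0.522²)/224 ≈ 9.43, so SE ≈ 3.07
- 9/3.07 − 1.96 ≈ 0.97, so power is about 83% by the normal approximation, in line with the statement.

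Only the 40 per site and the autocorrelations are used below.

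**Inputs from the document.** Utilities at 0, 3, 6, 9 and 12 months; 7 sites per arm; 40 per site; and, under Study Power, "a conservative intracluster correlation coefficient of 0.1, a cluster autocorrelation coefficient of 0.5, an individual autocorrelation coefficient of 0.6". Those autocorrelations are stated for the LEFS and are borrowed here for utility.

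**Assumptions not in the document.** Utility SD 0.15 to 0.25; utility ICC 0.01 to 0.10; correlation r of baseline with later utility 0.4 to 0.7 where the LEFS values are not used; 50,000 dollars per QALY as an illustration.

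**Step 1: share carried over.** The trapezoid weights over one year are 0.125, 0.25, 0.25, 0.25 and 0.125. The expected QALY shift per unit of baseline difference is therefore 0.125 + 0.875r: 0.475 at r = 0.4, 0.65 at 0.6 and 0.74 at 0.7, before the other covariates absorb some of it.

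**Step 2: r at arm level.** With the LEFS autocorrelations, r = [ICC × 0.5 + (1 − ICC) × 0.6/40]/[ICC + (1 − ICC)/40].

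**Step 3: chance imbalance.** With equal sites, the SD of the arm difference in baseline utility is SDu × √{(2/7)[ICC + (1 − ICC)/40]}.

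Entries with slashes are for SDu 0.15 / 0.20 / 0.25.

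| ICC | r | Share carried | Imbalance SD | QALY shift for one SD |
|---|---|---|---|---|
| 0.01 | 0.571 | 0.62 | 0.015 / 0.020 / 0.025 | 0.009 / 0.012 / 0.016 |
| 0.05 | 0.532 | 0.59 | 0.022 / 0.029 / 0.036 | 0.013 / 0.017 / 0.021 |
| 0.10 | 0.518 | 0.58 | 0.028 / 0.037 / 0.047 | 0.016 / 0.022 / 0.027 |

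Over the wider range r = 0.4 to 0.7, the shift runs from 0.0149 × 0.475 = 0.007 to 0.0468 × 0.7375 = 0.035 QALY, about 355 to 1,725 dollars per person. With site-size CV 0.7 and size-weighted means, the imbalance SD is SDu × √{2[1.49 × ICC/7 + (1 − ICC)/280]}, or 0.016 to 0.055.

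**Step 4: simulation.** 14 sites averaging 40 participants, random-intercept REML on the QALY, utility SD 0.20, autocorrelations 0.5 and 0.6, no true effect, no other covariates, 1,500 replicates per setting. Each cell gives the result without / with baseline utility in the model.

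| Sites | ICC | SD of QALY difference | Reduction | Share carried |
|---|---|---|---|---|
| Equal | 0.01 | 0.0163 / 0.0103 | 37% | 0.64 / −0.01 |
| Equal | 0.05 | 0.0229 / 0.0160 | 30% | 0.57 / −0.08 |
| Equal | 0.10 | 0.0300 / 0.0209 | 30% | 0.56 / −0.09 |
| CV 0.7 | 0.01 | 0.0169 / 0.0114 | 33% | 0.59 / −0.04 |
| CV 0.7 | 0.05 | 0.0245 / 0.0161 | 34% | 0.53 / −0.04 |
| CV 0.7 | 0.10 | 0.0309 / 0.0210 | 32% | 0.49 / −0.04 |

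With other covariates explaining 0 to 40% of the stable between-person variance, and r = 0.6, the share carried was 0.46 to 0.62 without baseline utility and −0.07 to +0.01 with it. The standard error fell to 0.63 to 0.70 of its former value. A further run at ICC 0.01 gave reductions of 33% with no covariate and 27% with one explaining 40%.

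**The case against.** The strongest reply is that nothing here invalidates the inference. Under randomization with even-handed recruitment, the QALY contrast is unbiased (the simulated mean difference was about zero) and the site-clustered interval already reflects chance imbalance. That stands: what remains is bias conditional on the realized imbalance and a loss of precision, in an analysis that is not the primary one.

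Systematic bias would need recruitment to differ between arms. The plan works against this: among other measures it states that "we did not reveal which study arm participants were in until after obtaining their consent". The risk is reduced, not removed, since clinic staff were not blinded. The document gives no evidence that the arms differ in utility.

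The size rests on assumptions, and no expected QALY or cost difference is given, so nothing shows that a cost-effectiveness conclusion would change. The top figure of 1,725 dollars pairs ICC 0.10 with r = 0.7. With the plan's cluster autocorrelation of 0.5, that end falls to about 1,350 to 1,390 dollars (individual autocorrelation 0.6 to 0.7). At ICC 0.01 with the plan's autocorrelations the range is about 470 to 780 dollars.

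Finally, some participants were identified at a clinical visit, and the document does not say whether baseline EQ-5D-5L always preceded first contact with the provider or disclosure of the arm. If it did not, adjusting for it could remove some early effect. The primary model's common baseline has the same exposure, so this is a caveat and not a reason to leave baseline utility out.

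**Conclusion.** The concern holds. Followed as written, the plan leaves baseline utility out of the QALY model. About half or more of a baseline difference would be carried into the QALY contrast under most of the assumptions examined, and the interval would be wider than it need be. The gain in precision survives realistic covariate adjustment.

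The size depends on utility SD, ICC and autocorrelation values that the document does not give. The point is confined to the cost-utility result: the LEFS and EQ-5D-5L effectiveness analyses already handle baseline through the constrained repeated-measures model. The change should be made, but the trial's main conclusion does not hang on it.

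**What to change.** State in the cost-utility paragraph that the QALY equation of the bivariate multilevel model includes each participant's baseline EQ-5D-5L utility in addition to the listed covariates. State also that the adjusted QALY difference feeds the incremental net benefit, the cost-effectiveness plane and the acceptability curves.

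The cost is one or two sentences and no new data. It should be done before analysis starts, because the same choice made after seeing the data would be post hoc. An individual-level covariate does not remove site-level imbalance exactly: the residual share was −0.01 to −0.09 with the plan's autocorrelations, and +0.09 to −0.14 with individual autocorrelation 0.4 to 0.7, against roughly 0.5 to 0.7 unadjusted. It would also help to say when baseline EQ-5D-5L was completed relative to first provider contact and disclosure of the arm.
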